Outcome(s):	
Primary results in the application area during application and over the course of up to one hour of post-application in 10-minute intervals (time 0min, 10min, 20min, 30min, 40min, 50min, 60min):
 
 - Perfusion of skin microcirculation (Laser Speckle Contrast Imager, High Power Laser Doppler), (ultrasound X-flow (baseline only and 60min post-application)) - Erythema formation (chromameter) 
 o of the skin o of the superficial muscles - Surface skin temperature (i-button, infrared thermometer, thermal imaging camera) 
 o of the skin - Oxygen Saturation (Near-Infrared Spectroscopy) 
 o of the superficial muscles - Subjective parameters 
 o Perceived temperature (-4 very cold to +4 very hot) o Thermal comfort (0 pleasant to 4 extremely uncomfortable) 
Secondary results within a 5cm radius of the application area during application and in the course of up to one hour of post-application in 10-minute intervals (time 0min, 10min, 20min, 30min, 40min, 50min, 60min):
 
 - Perfusion of skin microcirculation (Laser Speckle Contrast Imager, Ultrasound X-flow, High Power Laser Doppler) - Erythema formation (chromameter) 
 o of the skin o of the superficial muscles - Surface skin temperature (i-button, infrared thermometer, thermal imaging camera) 
 o of the skin - Oxygen Saturation (Near-Infrared Spectroscopy) 
 o of the superficial muscles - Subjective parameters 
 o Perceived temperature (-4 very cold to +4 very hot) o Thermal comfort (0 pleasant to 4 extremely uncomfortable)
Study design:	Randomized, controlled, clinical trial

SUPSI

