2.9 Early termination of the study

The sponsor or principal investigator may discontinue the study early if/

- ethical concerns
- insufficient number of subjects
- the safety of the participants cannot be guaranteed
- Findings from clinical practice make it pointless to continue the study
- early evidence or harm of the experimental intervention has been proven

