11 STATISTICAL METHODS

11.1 Hypotheses & Factors

*Local change in skin characteristics during and after a topical application of a **warming** product*

Perfusion of skin microcirculation

- H0 The perfusion of the skin microcirculation does not change significantly during and after the topical application of a warming product to the collateral side.
- H1 The perfusion of the skin microcirculation changes significantly during and after the topical application of a warming product to the collateral side.

Erythema formation

- H0 Erythema formation does not change significantly during and after topical application of a warming product to the collateral side.
- H1 Erythema formation changes significantly during and after topical application of a warming product to the collateral side.

Skin surface temperature

- H0The skin surface temperature does not change significantly during and after the topical application of a warming product to the collateral side.
- H1The skin surface temperature changes significantly during and after the topical application of a warming product compared to the collateral side.

Oxygen saturation of the superficial muscles

- H0The oxygen saturation of the superficial muscles does not change significantly during and after the topical application of a warming product to the collateral side.
- H1The oxygen saturation of the superficial muscles changes significantly during and after the topical application of a warming product to the collateral side.

Subjective temperature perceptions

- H0The subjective temperature perception does not change significantly during and after the topical application of a warming product to the collateral side.
- H1The subjective temperature perception changes significantly during and after the topical application of a warming product compared to the collateral side.

*Local change in skin characteristics during and after a topical application of a **cooling** product*

Perfusion of skin microcirculation

- H0 The perfusion of the skin microcirculation does not change significantly during and after the topical application of a cooling product to the collateral side.

SUPSI

- H1 The perfusion of the skin microcirculation changes significantly during and after the topical application of a cooling product to the collateral side.

Erythema formation

- H0 Erythema formation does not change significantly during and after topical application of a cooling product to the collateral side.

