11.4.2 Primary Analysis

The statistical data analysis will be carried out by [name] after completion of the data collection of the entire project.

Repeated measures analysis of variance (MANOVA)

2 factors:

Factor 1: Intervention (warming product versus control / cooling product versus control)

Factor 2: Time (baseline, 0min, 10min, 20min, 30min, 40min, 50min, 60min postal application)

The significance level is set at $P < 0.05$, and the statistical data analysis is carried out with SPSS V. 23.

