11.4.4 Interim analyses

The data is processed after the project ends. No additional interim analyses are planned.

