12.4 Audits and inspections

A report on the current status of the study is given orally to the study supervisor ([name]. [name]) on a monthly basis. This also includes demonstrating and presenting results and statistical analyses.

An annual report on the course of the study will be submitted to the CEC. Authorized persons of the CEC can view the data forms as well as the digital data on the institute's own computers at any time.

Data protection is guaranteed at all times.

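### Ten hypotheses share one unadjusted 0.05 level, skin temperature has no deciding device, and the statement that nothing is analysed before project end is contradicted elsewhere in the protocol

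*Combined protocol and SAP*

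**What the plan says.** **Hypotheses and level.** Section 11.1 sets out null and alternative pairs for perfusion, erythema, skin temperature, muscle oxygen saturation and subjective temperature, once for warming and once for cooling products. The alternatives are non-directional, for example "The perfusion of the skin microcirculation changes significantly during and after the topical application of a warming product to the collateral side". Section 11.4.2 names a two-factor repeated-measures analysis (treatment by eight time points) and a single level: "The significance level is set at $P < 0.05$, and the statistical data analysis is carried out with SPSS V. 23". It gives no multiplicity adjustment, hierarchy or lead outcome. Section 11.4.3 has no secondary analysis.

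**Devices.** The synopsis lists, among the primary results, "Surface skin temperature (i-button, infrared thermometer, thermal imaging camera" and does not say which device decides. Perfusion also has several instruments. Ultrasound X-flow is taken only at baseline and 60 minutes (synopsis), and section 5.1 places the high power laser Doppler in the sub-analysis. Thermal comfort is listed as a primary result but has no hypothesis in 11.1.

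**Timing of analysis.** Section 11.4.4 states: "The data is processed after the project ends. No additional interim analyses are planned". Section 12.4 provides a monthly oral report to the study supervisor and adds: "This also includes demonstrating and presenting results and statistical analyses". Section 2.9 lists among the reasons for stopping: "early evidence or harm of the experimental intervention has been proven". No boundary is attached. Table 1 places statistics in April to October 2018, before cooling data collection starts in March 2019. The study overview reports preliminary results for the three warming products and uses them to choose the sub-analysis product.

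**The concern.** With ten tests at 0.05 and no rule linking them, a report can present whichever outcome reached significance, and the stated 5% does not describe the chance that at least one such claim is false. Leaving the temperature device open adds choice inside one hypothesis: three instruments can disagree, and nothing says in advance which one settles it.

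The timing conflict is a second, distinct weakness. A reader of 11.4.4 would believe that no comparative result was seen before the end. Other sections show that warming results were seen and used, and that monthly presentation of analyses is foreseen. Choices made after that point, including the choice of device, cannot be assumed to be independent of the data.

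**Working it through.** **The plan's own figure.** The only figure is the per-test level of 0.05. No family-wise rate, power calculation or between-outcome correlation is given, so there is nothing further to reproduce. The level of 0.05 is the overall error for one test only.

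**Inputs.** Five hypotheses per class and two classes (11.1); 0.05 per test (11.4.2), two-sided because the alternatives are non-directional. The classes are different subjects and are treated as independent. All nulls are taken as true. Each hypothesis counts as one test, although 11.4.2 does not say which model term decides.

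**Independent tests.** The chance of at least one false positive among k tests is 1 − 0.95^k.

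- One class, k = 5: 1 − 0.95^5 = 0.226.
- Both classes, k = 10: 1 − 0.95^10 = 0.401.

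**Correlated tests** (simulated two-sided z-tests, equal correlation within a class):

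| Assumed correlation | Per class | Both classes |
|---|---|---|
| 0.5 | 18% | 33% |
| 0.8 | 13% | 24% |
| 0.9 | 10% | 19% |

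**Undesignated thermometers.** Count only readings that have a hypothesis in 11.1 and can fill the eight-level time factor: laser speckle, chromameter a*, three temperature devices, one saturation device and perceived temperature. That is 1 + 1 + 3 + 1 + 1 = 7 per class.

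- One class: 1 − 0.95^7 = 0.302.
- Both classes: 1 − 0.95^14 = 0.512.
- With correlation 0.5 between outcomes and 0.5 to 0.9 among the thermometers, simulation gives about 41% down to 37% over both classes.

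**Joint-test reading.** If the MANOVA label meant one joint test per class, the overall figure would be 1 − 0.95^2 = 0.0975.

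**Timing, passages side by side.** Section 11.4.4 allows nothing before project end. The overview reports product-level warming results and acts on them. Table 1 schedules statistics in 2018, while the project runs to December 2020. Section 12.4 presents analyses monthly, and 2.9 permits an early stop. These cannot all be correct. The protocol gives no look schedule, test or boundary, so no error rate can be attached to them.

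**Cost of the correction.** For a paired t-test with 45 pairs and 80% power, the detectable standardised difference is 0.427 at 0.05 and 0.530 at 0.01 (0.05/5, Holm's first step).

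**The case against.** **Exploratory purpose.** Section 10.3 describes the study as focused on basic findings, and no rule says that one significant outcome makes the study positive. Strict family-wise control is therefore partly a matter of judgement. This tempers the severity, but 11.1 still states formal hypotheses, they match the primary objectives in 4.2, and 11.4.2 tests them under the heading of primary analysis.

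**All nulls true.** This is unlikely for skin temperature with products chosen to warm or cool. The objection stands, and the figures are worst-case for that reason. It applies less to muscle oxygen saturation, because the overview reports no warming effect on deeper tissue and plans to look again.

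**MANOVA.** A joint test would reduce the problem. However, 11.1 poses one hypothesis per parameter, 11.4.2 describes no joint test, and two joint tests still give about 10%.

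**A larger figure is tempting.** A reader might count nine readings per class and infer 1 − 0.95^18 = 60%. The documents do not support that count. It needs X-flow, whose two time points cannot fill the time factor, and thermal comfort, which has no hypothesis. It also treats three readings of the same skin temperature as independent.

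**Repeated looks.** A reader might also treat the monthly reports as repeated significance tests; eight unadjusted looks at one hypothesis would give 17.6%. That models a formal test each month, at equal information steps, with stopping on significance. The protocol describes an oral report to a supervisor, a general list of stop reasons and no interim test. The reported warming results also fit analysis of a completed stage better than a look at accumulating data. The contradiction in the text stands; the number does not.

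**Conclusion.** The point holds. As written, the plan gives a family-wise error well above 5%: 22.6% per class and 40% over ten hypotheses if independent, falling to about 10–18% and 19–33% at assumed correlations of 0.9 to 0.5. Leaving the temperature device open raises the independent figures to 30% and 51%; that assumes any of the three thermometers could be taken to settle the hypothesis, which the plan neither states nor excludes. All figures assume true nulls and separate tests, and no single one is the true risk. The conclusion that the error exceeds 5% does not depend on which is used.

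The conflict between 11.4.4 and sections 12.4, 2.9, Table 1 and the overview is a defect in its own right. Its effect on error is unknown and should not be added to the figures above.

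**What to change.** 1. **Reconcile the measurements first.** For saturation, the synopsis names moorVMS-NIRS, 5.1 confines NIRS to the sub-analysis, and 9.1.2 names Moxy. The synopsis outcome list has the subjective scales at every follow-up, but its procedures section lists only measurements a to d there, which omits them.
2. **Name one deciding reading per hypothesis, available at all eight times:** laser speckle for perfusion, chromameter a*, one named temperature device, one saturation device, and perceived temperature. Choose on completeness, not on the 2017 results. Label all other readings supportive.
3. **Apply Holm over the five hypotheses within each class,** starting at 0.05/5 = 0.01. State that this controls 5% per class and leaves up to about 10% across both (1 − 0.95^2 = 9.75% for independent classes).
4. **State that for the warming class the choice was made after results were seen.** It can no longer be true pre-specification.
5. **Correct the timing text.** Limit the monthly reports in 12.4 to recruitment, data quality and safety. Amend 11.4.4 to say that the warming data were already analysed. Reconcile 2.9 with 11.4.4 on stopping for early evidence.

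**Cost.** These are text changes and need no extra subjects. Power falls: with 45 pairs the detectable effect rises from 0.43 SD to 0.53 SD at Holm's strictest step. That assumes a paired t-test and 80% power, neither of which the plan states.

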11.4.3 Secondary Analysis

Nonexistent.

11.4.4 Interim analyses

The data is processed after the project ends. No additional interim analyses are planned.

11.4.5 Security analyses

No security analyses are provided.

11.4.6 Deviations

Deviations from the planned statistical analysis are recorded and justified and reported to the CEC in the annual report.

11.5 Drop-outs and missing data

If a test subject does not complete the experiment, any data that has already been collected is destroyed and is not included in the final data analysis.

SUPSI

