7.4 Discontinuation of study participation

If a participant withdraws from the study, the lot of the allocation is returned to the pot in a new envelope and a new participant is sought.

All data collected to date will be evaluated as far as possible and included in the data analysis (in accordance with Art. 9 ClinO). After evaluation, the data is irreversibly anonymized.

The conditions for the termination of the experiment were described in chap. 5.4.

There is no disadvantage for the participants if they discontinue their participation in the study.

SUPSI

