8.5 Follow-up treatment of eliminated participants

Data already collected from eliminated participants will be destroyed and will not be included in the data analysis of the study.

There is no disadvantage for the participants if they discontinue their participation in the study and no further interventions are necessary for follow-up treatment.

If study participation was discontinued due to an excessive skin reaction occurring during study participation, this will be recorded and reported to the sponsor investigator (head of the research laboratory), study leader and supervisor of the study. If medical care is necessary, the report is forwarded to the business liability insurance of Thim van der Laan AG (Basler Versicherung) in order to ensure the appropriate follow-up treatment.

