9.1.6 Collection of data in case of early termination of studies

For the participants, there is no disadvantage in the event of an (arbitrary) discontinuation of study participation and no further interventions are necessary for follow-up treatment. The data collected to date will be evaluated as far as possible and included in the data analysis (in accordance with Art. 9 ClinO).

SUPSI

However, if study participation was discontinued due to an excessive skin reaction occurring during study participation, this will be recorded and reported to the sponsor investigator (head of the research laboratory), study management and supervisor of the study. In the event of necessary medical treatment, the report is sent to the business liability insurance of Thim van der Laan AG (Basler Versicherung).

The following are recorded:

- Date and time of the incident
- Course of the incident
- Persons involved & witnesses
- Study ID (specified by the CEC)
- Personal data of the person concerned (if not previously recorded)

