11.2 Sample size

The sample size in the literature varies greatly. The planned number of 105 subjects is within the wide range and is expedient, time-wise and financially feasible for the study.

11.3 Criteria for the statistical use of data in the case of incomplete data sets

Only data from subjects who have completed the entire protocol will be included in the study. This ensures that all data has been collected under the same conditions and thus remains homogeneous and comparable.

SUPSI

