11.4 Scheduled analyses

11.4.1 Datasets and Data Population

Only complete data sets will be included in the study. Data that contains only part of the protocol is not included in the analysis. No new test subject is being sought to replace the missing data.

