12.1.3 Archiving of data

The data collected will be kept for 10 years. Data protection will continue to be guaranteed.

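### The protocol both keeps and destroys the data of subjects who do not complete, and both replaces and does not replace them, so the analysed population is undefined

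*Combined protocol and SAP*

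**What the plan says.** **Data of subjects who stop: include.**
- Section 7.4: "All data collected to date will be evaluated as far as possible and included in the data analysis".
- Section 9.1.6: "The data collected to date will be evaluated as far as possible and included in the data analysis". Both sections cite Art. 9 ClinO.
- Section 10.3.1: if a listed side effect occurs, participation ends and the data are handled under 7.4 and 9.1.6.

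**Data of subjects who stop: destroy or exclude.**
- Section 8.5: "Data already collected from eliminated participants will be destroyed and will not be included in the data analysis of the study".
- Section 11.3: "Only data from subjects who have completed the entire protocol will be included in the study".
- Section 11.4.1 admits complete data sets only.
- Section 11.5: "any data that has already been collected is destroyed and is not included in the final data analysis".

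**Replacement.**
- Section 7.4: "the lot of the allocation is returned to the pot in a new envelope and a new participant is sought".
- Section 11.4.1: "No new test subject is being sought to replace the missing data".

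All of this is current text, and no section states which rule prevails.

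**The concern.** The first subject who does not finish triggers instructions that cannot all be obeyed, and one of them is irreversible. An analyst could choose a population after seeing the data and cite the protocol for the choice.

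The exclusion rule is also not neutral. Section 10.3.1 lists itching, redness and burning as side effects and ends participation when one occurs. Erythema, measured as the a* value, is a primary outcome (section 5.1). The subjects with the strongest skin response may therefore be the likeliest to leave the analysis. The untreated side does not correct for this, because both sides of an excluded subject are lost. Once the readings are destroyed, no sensitivity analysis can show whether the exclusion mattered.

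**Working it through.** **1. Can the rules be reconciled?** One might take the eliminated participants of 8.5 to be different from the withdrawn participants of 7.4. That does not help. Section 11.5 covers anyone who does not complete the experiment, and 11.3 admits completers only. A subject stopped under 10.3.1 has not completed, so 10.3.1 says include and 11.5 says destroy. For replacement, one might read 7.4 as covering withdrawals and 11.4.1 as covering technically incomplete records. The text does not say so, and a withdrawn subject's record is itself incomplete.

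**2. The plan's own figure.** The synopsis gives 45 + 45 + 15 = 105, which agrees with section 11.2. No power, effect size, SD or drop-out rate is given, so only the sum can be checked.

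**3. Size of the analysed population.** Inputs: 90 main subjects (synopsis and chapter 6) and a drop-out proportion d, which is assumed. Without replacement, the number of completers is 90(1 − d). With replacement until 90 complete, the number enrolled is 90/(1 − d), rounded up.

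| Reading | d = 0 | d = 5% | d = 10% | d = 20% |
|---|---|---|---|---|
| Exclude, no replacement (chapter 11) | 90 | 85.5 | 81 | 72 |
| Include, no replacement | 90 | 90 | 90 | 90 |
| Exclude, replace | 90 | 90 | 90 | 90 |
| Include, replace (7.4) | 90 | 95 | 100 | 113 |

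The two middle rows have equal counts but contain different people. At 10%, the first has 81 completers plus 9 partial records, and the second has 90 completers.

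**4. Possible bias under the chapter 11 rule.** Assume that a subject stops when a latent tendency exceeds its (1 − d) quantile, and that this tendency has correlation ρ with the response. The completers' mean then shifts by −ρ·φ(z)/(1 − d) SD, where z is the (1 − d) quantile of the standard normal. At d = 10%, φ(z)/(1 − d) = 0.195, so ρ = 0.3 gives 0.3 × 0.195 = 0.058 and ρ = 1 gives 0.195.

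| d | ρ = 0 | ρ = 0.3 | ρ = 1 |
|---|---|---|---|
| 5% | 0 | −0.033 | −0.109 |
| 10% | 0 | −0.058 | −0.195 |
| 20% | 0 | −0.105 | −0.350 |

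For a response such as redness, this shift is towards no effect.

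**5. Single missing readings (illustration only).** Assume 8 readings × 8 times × 2 sides = 128 readings per subject, missing independently. The proportion of subjects with at least one gap is then 1 − (1 − m)^128. This is 0.120 at m = 0.1% and 0.474 at m = 0.5%.

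**The case against.** The fair case on the other side is that drop-out may be rare. Subjects are healthy adults, the product is tested on the forearm beforehand, and measurement takes place on one day with about 100 minutes for the intervention. With no drop-out the conflict has no effect on the result. This stands as a limit on size. It does not make the rules compatible.

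A reader might draw several stronger conclusions that the documents do not support:
- **That a reacting subject is dropped and replaced by one who tolerates the product.** This joins the exclusion rule of chapter 11 to the replacement rule of 7.4. Chapter 11 says no replacement is sought, and 7.4 includes the data. It is one possible reading, not what the protocol prescribes.
- **That chapter 11 would prevail.** Nothing says so. For side-effect stops, the most specific text is 10.3.1, which points to inclusion.
- **That safety information is lost.** Sections 9.1.6, 10.3.1 and 10.3.3 require the incident to be recorded and reported. Only the measured readings would be destroyed.
- **That one missed reading costs 12% or 47% of subjects.** This takes the strictest reading of 11.4.1, an assumed missing rate and independence over 128 readings. The X-Flow ultrasound is taken only twice, so 128 is itself an assumption. If whole records are lost together, the loss falls to about 0.1% or 0.5%.
- **That destruction breaches archiving.** Section 12.1.3 says "The data collected will be kept for 10 years", but the destruction sentences can be read as exceptions to that general period. This adds little.

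**Conclusion.** The contradiction holds, on both data handling and replacement, and rests on the text alone. The analysis population is undefined and must be fixed before analysis. At an assumed 10% drop-out the analysed number is 81, 90 or 100, and at 20% it is 72, 90 or 113.

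The bias is conditional. It arises only if the exclusion rule is applied, drop-outs occur and stopping is related to response. The overlap between redness as a reason for ending participation and erythema as a primary outcome makes that link plausible. At 10% drop-out, the understatement is about 0.06 to 0.20 SD for ρ from 0.3 to 1, and zero if the two are unrelated. Both d and ρ are assumptions, so the actual size cannot be determined from the documents. The loss of any sensitivity analysis follows directly from destroying the readings.

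**What to change.** 1. Apply the data rule of 7.4, 9.1.6 and 10.3.1 throughout. Delete the destruction sentences in 8.5 and 11.5 and the completers-only rule in 11.3 and 11.4.1.
2. For each outcome, analyse every randomised subject with a baseline and at least one post-application reading, using a linear mixed model (SPSS MIXED) on all available readings. The repeated-measures (M)ANOVA in 11.4.2 needs complete records, so the inclusion rule cannot be carried out with it. For X-Flow, measured only at baseline and 60 minutes, an early stop leaves no post-application reading, and the report should say so.
3. Keep the completers analysis as a sensitivity analysis.
4. State one replacement rule. If a replacement is recruited, the withdrawn subject's data stay in the analysis.
5. Report the number of subjects already excluded, or whose data were destroyed, in the warming phase, with reasons. Table 1 schedules that data collection for 2017 and its statistics for 2018.

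The cost is protocol wording and a small amount of extra analysis in the software already named. The analysis change needs no extra subjects. Records already destroyed cannot be restored.
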